5. FOLLOW-UP AND OUTCOME MEASURES

5.1. Clinical assessments

5.1.1 Format

PROMs will be collected using a postal questionnaire at baseline, at three and six months.

The postal questionnaires will be sent from the NOTABLE Trial Office with postage paid envelopes two weeks before the due date. Reminders will be sent to the participants if the questionnaire is not returned within one week of the due date and attempts will be made to contact the women by phone if the questionnaire is not returned by two weeks after the due date.

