5.1.2 Timing of assessments

The primary outcome will be measured clinically at the end of the surgical procedure. In addition PROMs will take place the evening of the surgical intervention (return home), during the first postoperative week (pain by VAS scores and medication) and at 3 and 6 months (dyspareunia and sexual wellbeing). Clinical physician assessment will take place the evening of the surgical intervention (return home) and during the first six weeks following surgery (pelvic infection, surgical complications).

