5.3. Secondary clinical outcome measures

We will measure the following secondary outcomes:

- The proportion of women discharged the same day based on their own preference, as a dichotomous outcome. The decision to discharge from the day care unit or to admit to hospital for the night will be based solely on the choice of the woman to return home the same day or stay overnight. The outcome assessor will report this decision in the patient record without consulting the results of the pain scoring or whether or not additional

analgesics were administered. In case of conflict (women wishing to return home against outcome assessor's advice based on clinical suspicion of possible complications for instance) the study participant is not excluded from further follow-up. Data will be analysed using a sensitivity analysis by imputing that the index participant would have agreed to stay overnight as dictated by the clinical judgement of the outcome assessor versus the available data analysis.

- Postoperative pain scores, as an ordinal outcome, measured using a VAS scale twice daily from day 1 till 7 self-reported by the participating women: one measurement will be done in the morning after bed rest at night (rest) and the other will be done in the evening before going to bed after physical activity (active). The participants should place the cursor of the VAS scale device available at the day care unit of the participating centre on the picture indicating the expression of pain sensation that according to their own experience best describes how they feel pain at the time point of measurement. By looking at the back of the scale they can measure the level of pain by recording the numbers immediately to the left and right of the red line: e.g. pain level 0 to 1, or pain level 5 to 6. The lowest number will be recorded by the outcome assessor for data analysis. The reliability of VAS has been established in the assessment of chronic gynaecological conditions like pain.

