6.3. Statistical Analysis

We will calculate a 95% confidence interval of the difference in the proportions of women with a successful removal of an adnexal cyst. Non inferiority of the intervention (vNOTES) will be concluded

when 15% lies above the upper limit of this confidence interval. For this primary analysis, adjustments for prognostic factors will not be made in the first instance; the effect of the variables listed in Section 3.5 (Stratification of randomisation) will be explored as a secondary analysis. Continuous measures (VAS scores) will be analysed using analysis of covariance (adjusting for baseline value). Multilevel models for repeated measurements will also be used to compare the mean differences in VAS pain scores between groups overall at all time points, thereby maximising the power of the data available.

Analysis will be performed on an 'intention to treat' basis in the first instance as recommended in the CONSORT statement. A 'per protocol' analysis will also be performed to test the robustness of the results obtained. As a conservative measure, estimates of effect sizes between the two arms will be presented as point estimates with two-sided 95% confidence intervals. The trial can only conclude non-inferiority if 15% lies out of the upper band of the confidence interval (i.e. vNOTES 15% less successful than laparoscopic treatment).

Baseline characteristics of the patients enrolled in the two groups will be compared to ensure that randomisation has produced comparable groups of participants, and will be covariates in the modelling procedure.

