3. POSTOPERATIVE PHASE**RECOVERY**

- If VAS >4: 1g Paracetamol IV
- Reevaluation after 30min.
 - If VAS >4: 2,5mg Piritramide IV

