APPENDIX VI VAS scale

APPENDIX VII: Participant's pain log book

NOTABLE trial

First & last name:	
Date of surgical procedure:	

Arrival at home:

Time of arrival at home:

Pain score:

0	1	2	3	4	5	6	7	8	9	10

Pain medication:

	Dose in mg	Number of tablets	Time intake
Paracetamol			
Ibuprofen			
Other			

Day 1 after surgery:

Pain score morning:

0	1	2	3	4	5	6	7	8	9	10

Pain score evening:

0	1	2	3	4	5	6	7	8	9	10

Pain medication:

	Dose in mg	Number of tablets	Time intake
Paracetamol			
Ibuprofen			
Other			

Day 2 after surgery:

Pain score morning:

0	1	2	3	4	5	6	7	8	9	10

Pain score evening:

0	1	2	3	4	5	6	7	8	9	10

Pain medication:

	Dose in mg	Number of tablets	Time intake
Paracetamol			
Ibuprofen			
Other			

Day 3 after surgery:

Pain score morning:

0	1	2	3	4	5	6	7	8	9	10

Pain score evening:

0	1	2	3	4	5	6	7	8	9	10

Pain medication:

	Dose in mg	Number of tablets	Time intake
Paracetamol			
Ibuprofen			
Other			

Day 4 after surgery:

Pain score morning:

0	1	2	3	4	5	6	7	8	9	10

Pain score evening:

0	1	2	3	4	5	6	7	8	9	10

Pain medication:

	Dose in mg	Number of tablets	Time intake
Paracetamol			
Ibuprofen			
Other			

Day 5 after surgery:

Pain score morning:

0	1	2	3	4	5	6	7	8	9	10

Pain score evening:

0	1	2	3	4	5	6	7	8	9	10

Pain medication:

	Dose in mg	Number of tablets	Time intake
Paracetamol			
Ibuprofen			
Other			

Day 6 after surgery:

Pain score morning:

0	1	2	3	4	5	6	7	8	9	10

Pain score evening:

0	1	2	3	4	5	6	7	8	9	10

Pain medication:

	Dose in mg	Number of tablets	Time intake
Paracetamol			
Ibuprofen			
Other			

Day 7 after surgery:

Pain score morning:

0	1	2	3	4	5	6	7	8	9	10

Pain score evening:

0	1	2	3	4	5	6	7	8	9	10

Pain medication:

	Dose in mg	Number of tablets	Time intake
Paracetamol			
Ibuprofen			
Other			

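### First-week pain cannot be analysed by ANCOVA adjusted for baseline as section 6.3 is written, because no preoperative general pain VAS is scheduled

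*Protocol*

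**What the plan says.** Section 6.3 sets the analysis: "Continuous measures (VAS scores) will be analysed using analysis of covariance (adjusting for baseline value"). It continues: "Multilevel models for repeated measurements will also be used to compare the mean differences in VAS pain scores between groups", over all time points.

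The measurement schedule is set elsewhere:

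- Section 5.3 has pain "measured using a VAS scale twice daily from day 1 till 7 self-reported by the participating women", one reading in the morning and one in the evening.
- Section 5.1.2 places it "during the first postoperative week (pain by VAS scores and medication").
- The log book in Appendix VII opens with a pain score beside the field "Time of arrival at home", then has morning and evening scores for days 1 to 7.
- The pain protocol in Appendix V uses a VAS in the recovery room to trigger analgesia ("If VAS >4: 1g Paracetamol IV").

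Section 5.3 names a baseline for three other outcomes: dyspareunia (prevalence and intensity), the SSFS and the EQ-5D-3L. It names none for general pain.

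**The concern.** The analysis section requires a measurement that the schedule does not provide. A statistical analysis plan can choose among models, but it cannot supply a preoperative score that nobody recorded. The gap therefore belongs to the protocol.

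Pain in the first postoperative week is a named secondary question (section 1.6), and less pain is one of the benefits put forward for vNOTES (Summary, section 1.4.3). An analyst who follows section 6.3 must either drop the adjustment after the data are in or take some early postoperative score as the baseline. The first is an unplanned change. The second conditions on a value that surgery has already affected. The arrival-home score has a further weakness: its timing depends on whether the woman goes home the same day, which is itself a secondary outcome.

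**Working it through.** **Step 1: is there a preoperative general pain VAS?** Section 6.3 gives no figure to reproduce here, so the check sets the passages side by side.

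| Place in protocol | Measure | Before surgery? |
|---|---|---|
| Summary; section 5.3 | Pain VAS, days 1 to 7 | No |
| Section 5.1.2 | Pain VAS, first postoperative week | No |
| Appendix V | Recovery-room VAS | No |
| Appendix VII | Arrival at home, then days 1 to 7 | No |
| Section 5.3; Appendix VIII | Dyspareunia, 0 to 10 | Yes, but pain during sexual activity |
| Section 5.3; Appendix IX | SSFS | Yes, but sexual functioning |
| Section 5.3; Appendix X | EQ-5D-3L | Yes, but a three-level pain item and a 0 to 100 health scale |

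The measures with a baseline differ from the pain VAS, so none of them is its baseline value. No general pain VAS is taken before surgery.

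**Step 2: what would a postoperative score used as baseline do?** This is an illustration of something the protocol does not propose. The inputs come from the randomised trial of umbilical versus vaginal specimen retrieval summarised in section 1.4.1:

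- 3 hours: 2.4 vs 1.4, SD 2.0 in each arm. Difference 1.0. This stands in for the early score.
- 24 hours: 1.1 (SD 1.5) vs 0.5 (SD 1.4). Difference 0.6. Pooled SD = √((1.5² + 1.4²)/2) = √2.105 = 1.45. This is the outcome.

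With within-arm correlation ρ between the two scores (assumed; the protocol gives none), the slope is b = ρ × 1.45/2.0, and the expected ANCOVA estimate is 0.6 − b × 1.0.

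| ρ (assumed) | b | Expected estimate | Share of 0.6 lost | Simulation mean |
|---|---|---|---|---|
| 0.3 | 0.218 | 0.38 | 36% | 0.385 |
| 0.5 | 0.363 | 0.24 | 60% | 0.236 |
| 0.7 | 0.508 | 0.09 | 85% | 0.093 |

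The simulation used 2,000 runs with 28 women per arm, close to 66 × 0.85 / 2 = 28.05.

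**Step 3: what would a true preoperative score do?** Under randomisation it leaves the expected difference at 0.6 and multiplies the residual variance by 1 − r². At assumed correlations of 0.3 to 0.5 with later pain, the reduction is 0.3² = 9% to 0.5² = 25%. Omitting it costs precision and introduces no bias.

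**The case against.** The strongest reply is that section 6.3 says VAS scores in general, and only the following sentence narrows to pain. Dyspareunia intensity is also scored on a VAS and has a baseline, so the ANCOVA can be run there. This stands, and it limits the point to first-week pain. It does not clear the sentence, because the repeated-measures model is described as an additional analysis of the same kind of score and nothing exempts postoperative pain from the ANCOVA.

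Section 5.1.1 says "PROMs will be collected using a postal questionnaire at baseline, at three and six months", and section 5.1.2 counts first-week pain among the PROMs, so a baseline pain score might be thought implied. The evidence is weak. That sentence describes the postal schedule, whereas first-week pain is recorded in a log book that starts after surgery.

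A reader might also infer that the protocol intends a postoperative score as baseline, or that the first log-book score is the only candidate. The documents support neither. No section says which value would serve, and the recovery-room VAS is earlier and does not depend on discharge, although it too is postoperative.

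Finally, the repeated-measures model needs no baseline score, so the pain question remains answerable. This is correct and reduces the weight of the point.

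**Conclusion.** The point holds for first-week postoperative pain: the baseline-adjusted ANCOVA in section 6.3 cannot be run as written, because the schedule contains no preoperative general pain VAS. It does not hold for dyspareunia intensity.

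The loss of about 36% to 85% of a 0.6-point difference is conditional. It would arise only if an early postoperative score were used as the baseline. It also rests on assumed correlations of 0.3 to 0.7 and on pain figures from a trial of specimen retrieval routes after laparoscopy, not of vNOTES. A reader might conclude that most of the effect would always disappear. At the lower correlation that is not so, since 64% of the difference remains (0.382/0.6).

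This is a contradiction between planned analysis and planned data for one secondary outcome, and it should be corrected. The primary non-inferiority comparison is untouched.

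**What to change.** Choose one of two routes.

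1. Record one general pain VAS on admission, before surgery. Add it to sections 5.1.2 and 5.3 and to the log book or case report form, and name it in section 6.3 as the covariate for both the ANCOVA and the multilevel model. The cost is one short extra reading per woman, with a device that section 5.3 already places at the day care unit. Since both symptomatic and asymptomatic women are eligible (section 3.2), preoperative pain may vary enough for the reading to be useful.
2. Restrict baseline-adjusted ANCOVA in section 6.3 to outcomes with a stated baseline, such as dyspareunia intensity. Analyse first-week pain with the repeated-measures model already planned, treating every postoperative score as an outcome. This is a wording change only and gives up the possible gain in precision.

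Under either route, add a sentence saying that no score taken after surgery (recovery room, arrival at home or day 1) will be used as a baseline covariate.

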6.3.1 Subgroup analyses

Subgroup analyses are limited by statistical power and can produce spurious results particularly if many are undertaken. We will not undertake any subgroup analyses in this pilot study.

6.3.2 Proposed frequency of analyses

1. Twice yearly review of recruitment, compliance and loss to follow-up for NOTABLE Trial Steering Committee.
2. Annual interim analyses of effectiveness for confidential review by Ethics Committee to determine whether the principal question has been answered and to monitor adverse events.
3. Main analyses of effectiveness of NOTABLE once all participants have reached 6-month follow up of the total study sample.
4. Additional analysis of longer term effects (completion of one and two years of follow-up).

6.3.3 Handling missing data

The interpretation of missing values in the analysis of clinical trials can be fraught with danger. The methods used to allow for missing data make assumptions about the reasons for data not being present, such as in the "observed case" analysis, where the presence or absence of data is viewed as unrelated to outcome, or in the "Last Observation Carried Forward" analysis where the assumption is that the condition does not improve or worsen following withdrawal from follow-up. To minimise possible biases, participants will continue to be followed up even after protocol treatment violation.

Missing data items will be imputed from given values if limited to a single item response. If a form is missing entirely or greater than one item imputation will not be attempted. Sensitivity analyses will be carried out to determine whether or not the results obtained are robust to the methods used to handle missing data. These approaches are in line with the recent recommendations from the European Agency for the Evaluation of Medicinal Products.

Questionnaires will only be treated as late if they are returned after the subsequent questionnaire has been sent to the participant. However if this form is the only form available at the later time point it will be included at the subsequent time.

6.4. Health Economic Analysis

6.4.1 Form of the economic evaluation

If vNOTES is found to be an effective treatment for the removal of benign adnexal mass, then it is likely that there can be cost implications for the health care sector. For example, as the woman will be treated as an outpatient, thus avoiding an inpatient stay, resources may be saved. However, vNOTES may incur costs due to equipment required and the specialist nature of health care professionals to perform this procedure. Therefore all costs incurred by both procedures need to be assessed in conjunction with measures of effectiveness.

The aim of the economic evaluation is to determine the cost-effectiveness of vNOTES compared with standard laparoscopic treatment. Although the trial has been designed as a non-inferiority trial, we feel the most appropriate type of analysis is a cost-effectiveness analysis. Cost-effectiveness will be determined in two ways. A cost-effectiveness analysis will be undertaken to calculate the cost per additional cured case adnexal removal at six months, utilizing the clinical outcome data collected within the trial. In addition, a cost-utility analysis will be undertaken to calculate the cost per additional quality-adjusted life year (QALY) gained. The utility values required to calculate QALYs will be obtained by administering the EuroQol EQ-5D-3L questionnaire to all study patients at baseline, three months and six months. In the first instance, the evaluation will consider costs incurred by the health service in the delivery of both treatment pathways. However, information on costs incurred by patients will also be collected in order that an evaluation from a wider societal perspective can also be undertaken.

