Given its potential benefits, including no visible scars, fewer port-related complications, and less painful and faster post-operative recovery, we have introduced transvaginal pure NOTES (vNOTES) for the treatment of benign adnexal masses in our surgical practice since November 2013. A case-series by our group describing the technical feasibility of removing benign adnexal masses by vNOTES in 20 women has been published recently (7). Most women reported a low postoperative pain score (range 0 to 2) measured at day 1 following surgery by a visual analogue scale (VAS). Based on these preliminary observational findings we decided to design a pilot randomized trial to study the effectiveness of the new vNOTES approach based on the hypothesis that the new technique is at least as effective for removing a benign adnexal mass without cyst rupture compared to the classical laparoscopic technique.

Objective: To compare vNOTES and established laparoscopic removal of benign adnexal masses

Study design: Randomised controlled/single centre/single-blinded/parallel-group/non-inferiority/efficacy trial.

Study population: Women with symptomatic or persistent benign adnexal masses detected by clinical examination and ultrasound.

Randomisation: After assessment of eligibility/ informed consent women will be randomly allocated to undergo one of two techniques for removal of the benign adnexal mass before surgery by using a computer generated randomisation list. We will use stratified randomisation according to the cyst diameter.

Intervention: Women will be treated by a surgeon who is not blinded to the treatment allocation and who is equally skilled in performing both techniques. In the intervention group a vNOTES technique will be used.

Control: In the control group surgery will be done by a classical laparoscopic technique.

Participants, nursing staff and outcome assessors will be blinded by the use of mock surgical skin incisions. Pre- and postoperative treatment will be provided by staff blinded for the allocated intervention using a standardized protocol that is identical for both techniques. All women will be advised not to work during a 4-week period and to abstain from sexual intercourse until their 6-week booked appointment for a postoperative assessment.

Main study parameters/endpoints:

Primary outcomes: successful removal of a benign adnexal mass without spill.

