4. TREATMENT ALLOCATIONS

4.1. Surgical procedures

The principal investigator, who has training and experience in both laparoscopy and NOTES, will perform all surgical procedures. He is therefore not blinded. All vNOTES participants will be blinded by three superficial “mock” skin incisions similar to those routinely done with the laparoscopic technique. The wound bandages will be left in place until the day 7 postoperative control to be removed by the coordinating investigator who will state at that moment that the wound healing has left an almost invisible scar as expected. This procedure aims to blind the participants, personnel and outcome assessors. The practice of performing “mock” incisions should not be considered as unethical: it is a procedure that has already been used in some surgical trials to minimise performance and detection bias whenever a subjective outcome is measured (22). The decision to use “mock” surgery is based on the clinical equipoise regarding the balance between benefits and adverse events for the two interventions under comparison (23).

4.1.1 vNOTES adnexectomy

This is the surgical procedure done in the intervention arm of the NOTABLE trial.

Clindamycin vaginal cream is administered on admission of the study participant to the outpatient ward.

The patient is placed in lithotomy position in a vacuum mattress. The abdomen, the vulva and the vagina are disinfected with an alcoholic betadine solution and draped. A Foley catheter is inserted into the bladder.

Three superficial skin incisions are made, one deep in the umbilicus and one in the left and right iliac fossa lateral of the epigastric vessels, and in the suprapubic region. The small vertical intraumbilical skin incision is closed with a monocryl 3/0 intradermal suture. Wound bandages are applied to all three skin incisions.

A 2.5 cm posterior colpotomy is made using a cold knife. The pouch of Douglas is opened using cold scissors. A Gelpoint Mini (Applied Medical) is used as vNOTES port and is inserted into the pouch of Douglas. CO₂ is insufflated until a maximal intraperitoneal pressure of 15mmHg. An optic is inserted and the peritoneal cavity is inspected. The patient is now placed in Trendelenburg position. The small intestine is lifted out of the pelvis.

The ureter is identified, but not routinely dissected. It is only dissected if it cannot be identified transperitoneally. The proximal end of the Fallopian tube is coagulated at its origin into the uterus

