- Postoperative pain defined by the total use of analgesics during the first week following surgery as described in the standardized pain treatment protocol, as an ordinal outcome. The use of pain medication following surgery should be reported in the nursing file. At home the participants should note in their participant log book the name, dosage, route of administration of any analgesic drug that was taken from the moment they are at home until the assessment on day 7 irrespective of whether this was done on their own initiative or after consulting a family physician or any other medical specialist. The assessment of the total use of analgesics will be done on day 7 by the outcome assessor (the coordinating investigator), who is blinded for the intervention done by the principal investigator.
- Postoperative infection defined by lower abdominal pain with fever $> 38^{\circ}\text{C}$ and positive clinical signs or laboratory findings, detected during the first six weeks of surgery, as a dichotomous outcome.
- Per- or postoperative complications according to the Clavien- Dindo classification detected during the first six weeks of surgery, as a dichotomous outcome (Appendix III).
- Hospital readmission during the first six weeks of surgery, as a dichotomous outcome.
- Incidence and intensity of dyspareunia recorded by the participants at 3 and 6 months by self-reporting using a simple questionnaire and VAS scale, as a dichotomous and ordinal

outcome. A measurement of the prevalence and the intensity of dyspareunia will be done at baseline assessment.

- Sexual wellbeing at baseline, at 3 and 6 months by self-reporting the SSFS.
- Quality of life at baseline, at 3 and 6 months by self-reporting the EQ-5D-3L questionnaire.
- Duration of surgery measured as the time in minutes from the insertion of the bladder catheter to the end of vaginal/abdominal wound closure, as a continuous outcome.

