APPENDIX X: EQ-5D-3L Health questionnaire

Health Questionnaire
English version for the UK
(Validated for Ireland)

Sample

By placing a tick in one box in each group below, please indicate which statements best describe your own health state today.

Mobility

- I have no problems in walking about
- I have some problems in walking about
- I am confined to bed

Self-Care

- I have no problems with self-care
- I have some problems washing or dressing myself
- I am unable to wash or dress myself

Usual Activities (e.g. work, study, housework, family or leisure activities)

- I have no problems with performing my usual activities
- I have some problems with performing my usual activities
- I am unable to perform my usual activities

Pain / Discomfort

- I have no pain or discomfort
- I have moderate pain or discomfort
- I have extreme pain or discomfort

Anxiety / Depression

- I am not anxious or depressed
- I am moderately anxious or depressed
- I am extremely anxious or depressed

To help people say how good or bad a health state is, we have drawn a scale (rather like a thermometer) on which the best state you can imagine is marked 100 and the worst state you can imagine is marked 0.

We would like you to indicate on this scale how good or bad your own health is today, in your opinion. Please do this by drawing a line from the box below to whichever point on the scale indicates how good or bad your health state is today.

Your own health state today

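### With EQ-5D-3L only at baseline, 3 and 6 months, the QALY estimate can register late differences but not an early recovery gain, although perioperative costs are counted

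*Protocol*

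**What the plan says.** Section 6.4.1 of the protocol promises that "a cost-utility analysis will be undertaken to calculate the cost per additional quality-adjusted life year (QALY) gained", with utilities obtained by "administering the EuroQol EQ-5D-3L questionnaire to all study patients at baseline, three months and six months". Section 5.3 gives the same times ("Quality of life at baseline, at 3 and 6 months by self-reporting the EQ-5D-3L questionnaire"), and so does section 5.1.1 for the posted forms ("PROMs will be collected using a postal questionnaire at baseline, at three and six months"). The schedule is consistent throughout.

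The questionnaire in Appendix X has a same-day recall: "please indicate which statements best describe your own health state today".

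The Summary and section 1.4.3 give as reasons for introducing vNOTES "no visible scars, fewer port-related complications, and less painful and faster post-operative recovery". Section 1.6 asks about pain in the first postoperative week. It also asks about dyspareunia, quality of life and sexual wellbeing at 3 or 6 months.

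Two early contacts are already planned. Bandages stay on "until the day 7 postoperative control" (section 4.1), and women abstain from intercourse "until their 6-week booked appointment for a postoperative assessment" (Summary). Women also fill in a pain log book from arrival at home to day 7 (Appendix VII).

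On the cost side, section 5.4 collects the procedure, equipment, drugs, inpatient stay, readmissions and re-treatments and, for the wider perspective, time lost from work.

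**The concern.** Part of the case for vNOTES is an early gain: milder pain and a quicker recovery. No utility is measured between the preoperative form and 3 months. The measures taken in that window are pain VAS and analgesic use to day 7, the discharge choice, and infection, complications and readmission to 6 weeks. None of these is a utility.

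The two halves of the cost per QALY are then treated unequally. The resources used around the operation enter the numerator, but the health experienced in those weeks does not enter the denominator. A ratio is sensitive to this, because replacing a small gain by zero changes the result even when the gain is modest. The collection schedule is fixed in the protocol, so no later analysis plan can restore responses that were never collected.

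**Working it through.** The protocol states no QALY figure, utility value or QALY formula, so there is no figure of its own to reproduce.

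**Inputs from the protocol**
- EQ-5D-3L times: 0, 0.25 and 0.5 years (sections 5.3 and 6.4.1).
- Recall: the day of completion (Appendix X).
- Existing contacts: log book to day 7 (Appendix VII), day-7 control (section 4.1), 6-week appointment (Summary).
- Size: 66 women, or 33 per arm; 27 per arm before the drop-out allowance (section 6.1).

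**Assumptions**
- QALYs are a trapezoidal area under the utility curve.
- The between-arm utility gap is zero before surgery and takes assumed values afterwards.

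**1. Early gain that exists under the assumptions**

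Gain = gap in week 1 × 7/365 + gap in weeks 2 to 6 × 35/365.
- Small (0.05, then 0): 0.05 × 7/365 = 0.0010
- Middle (0.10, then 0.02): 0.10 × 7/365 + 0.02 × 35/365 = 0.0038
- Large (0.20, then 0.05): 0.20 × 7/365 + 0.05 × 35/365 = 0.0086

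**2. What the planned schedule records**

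If the gap has gone by 3 months, the gaps at 0, 3 and 6 months are 0, 0 and 0:

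0.25 × (0 + 0)/2 + 0.25 × (0 + 0)/2 = 0 in all three cases.

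The trapezoid is assumed, but any method that uses only these three points has no information on the weeks between surgery and 3 months.

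**3. What the schedule does record**

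An assumed difference of 0.02 at both 3 and 6 months gives 0.25 × (0 + 0.02)/2 + 0.25 × (0.02 + 0.02)/2 = 0.0075 QALY. A late difference is therefore counted, and it can be as large as the early amounts missed.

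**4. Size against precision**

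Assume a 6-month QALY SD of 0.03 to 0.10. The standard error of the difference is SD × √(2/n).
- Best case: 0.03 × √(2/33) = 0.007
- Worst case: 0.10 × √(2/27) = 0.027

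The missed 0.001 to 0.009 is at most about one standard error, and usually much less.

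**5. What added forms would recover**

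With forms at days 7 and 42, and no gap at day 91:

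estimate = [7 × d7/2 + 35 × (d7 + d42)/2 + 49 × d42/2] / 365.

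Days 7 and 42 are the edges of the assumed steps, so each can be read on either side of the step.

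| Scenario | True | Lower reading | Upper reading |
|---|---|---|---|
| Small | 0.0010 | 0 | 0.0029 |
| Middle | 0.0038 | 0.0012 | 0.0081 |
| Large | 0.0086 | 0.0029 | 0.0173 |

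For the middle scenario, the lower reading is (7 × 0.01 + 35 × 0.01)/365 = 0.42/365. The upper reading is (7 × 0.05 + 35 × 0.06 + 49 × 0.01)/365 = 2.94/365.

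A smooth decline behaves better. A gap of 0.10 falling linearly to zero over 4 weeks is truly 0.10 × (4/52)/2 = 0.0038. At week 1 it is 0.075 and at week 6 it is 0, so the estimate is (1 × 0.0375 + 5 × 0.0375)/52 = 0.0043.

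A gap gone by day 7 is still recorded as zero. One earlier form, at day 3 for illustration, changes the lower reading of the small scenario from 0 to (3 × 0.025 + 4 × 0.025)/365 = 0.0005. Its upper reading is (3 × 0.025 + 4 × 0.05 + 35 × 0.025)/365 = 0.0032. The added points help, but the interpolation rule still matters.

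**The case against.** The strongest reply has four parts.

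**Late effects are measured.** A reader might infer that every QALY difference between the techniques would fall in the unmeasured weeks, or that the trial cannot answer its cost-utility question at all. The protocol supports neither inference. Section 1.6 asks about dyspareunia, quality of life and sexual wellbeing at 3 or 6 months, and EQ-5D-3L is taken at exactly those times. Only one component of the QALY difference is lost.

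**The amount is small and assumed.** This stands. The documents contain no utilities, and some of their content points to the low end:
- In the cited randomised trial of specimen retrieval routes, mean pain at 24 hours was 1.1 against 0.5 on a 10-cm scale, a gap of 0.6 (section 1.4.1). This is indirect evidence, because that trial compared extraction routes only.
- Both arms are advised not to work for 4 weeks.
- vNOTES women also receive skin incisions.
- EQ-5D-3L has three levels per item.

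**Early recovery is visible elsewhere.** Pain and analgesic use are measured directly, and inpatient stay, medication and lost work are costed. This is true, but none of it supplies the utility that a QALY needs.

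**Two added forms are imperfect.** This also stands. The table shows possible under- and overestimation, and a gap gone by day 7 would be missed. It is a reason for an earlier form and a stated interpolation rule. It does not make the present schedule adequate.

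Finally, this is a secondary analysis in an unfunded pilot that aims for minimal workload, which limits the weight of the point.

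**Conclusion.** The point holds in a limited form. The schedule is one-sided in time: it can register differences present at 3 or 6 months, but not an early recovery gain that has gone by then. Perioperative costs are counted, so the cost per QALY is biased towards no early utility gain.

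Under the assumed gaps the missed amount is about 0.001 to 0.009 QALY. This is small against a standard error of roughly 0.007 to 0.027, which itself rests on an assumed SD. The zero recorded by the planned schedule does not depend on the size of the gap, only on the gap having closed by 3 months.

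The primary outcome, the sample size and the non-inferiority conclusion are unaffected. The protocol does not contradict itself here. The fault is a collection schedule poorly matched to one of the analyses it serves. It is worth correcting because the data cannot be recovered later and the correction is cheap.

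**What to change.** 1. Add EQ-5D-3L at the day-7 control, completed before the bandages are removed so that the sight of the wounds does not influence the answers, and at the 6-week appointment.
2. Add one form in the first days after surgery, placed in the pain log book. Without it, a difference gone by day 7 is still missed.
3. State in section 6.4 that QALYs are the area under the curve through all these points, with a sensitivity analysis on the interpolation between them.
4. Bring sections 5.1.1, 5.1.2, 5.3 and 6.4.1 into line with the new times.

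The cost is up to three short extra forms per woman. No extra visits or staff are needed, and section 5.4 records that free use of the questionnaire has been approved.

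If the forms are not added, section 6.4 should state that the QALY estimate excludes early recovery, so that a null utility result is not read as evidence that recovery was the same in both arms.
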